6.11. Efficacy Analyses

The secondary efficacy objectives will be addressed by conducting MMRM analyses (as described in [Section 6.10](#), but without the baseline score in the model for CGI-I and PGI-I, and week will be replaced by visit except for items from diary) to compare treatment differences for the following variables:

- From the BPI-SF, each of the 4 questions assessing the severity of worst pain, least pain, and average pain in the past 24 hours, and the pain right now
- From the BPI-SF, each of the 7 questions assessing the interference of pain with activities and the mean of the seven questions
- Weekly mean of night pain and worst pain scores measured using 11-point NRS in the daily patient diary
- BDI-II total score
- CGI-I and PGI-I

For the NPSI questionnaire, the total score and each of the 5 subscores: burning spontaneous pain, pressing spontaneous pain, paroxysmal pain, evoked pain, and paresthesias/dysesthesias will be addressed by ANCOVA analysis (as described in [Section 6.10](#)) to compare treatment differences. Missing data will be imputed using LOCF method.

Further secondary objectives will be addressed by comparing treatment groups with respect to the proportions of patients achieving each of the following at Visit 6 (Week 12) using Fisher's exact test. In this analysis, missing data will be imputed using LOCF method:

- A $\geq 30\%$ reduction on the weekly mean of the 24-hour average pain score measured using an 11-point NRS in the daily patient diary
- A $\geq 50\%$ reduction on the weekly mean of the 24-hour average pain score measured using an 11-point NRS in the daily patient diary

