#### 9.3. Method of Assignment to Treatment

Patients who meet all criteria for enrollment will be randomized to double-blind treatment at Visit 2. Assignment to treatment groups will be determined by a computer-generated random sequence using an interactive web-response system (IWRS). The IWRS will be used to assign blisterpacks containing double-blind study drug to each patient. The appropriate number of blisterpacks will be dispensed at Visit 2, Visit 4, and Visit 5, depending on each dose regimen. Site personnel will confirm that they have located the correct blisterpacks by entering a confirmation number found on the blisterpacks into the IWRS.

Randomization will be stratified by baseline weekly mean of the 24-hour average pain score measured using the 11-point NRS in the dairy patient diary ( $<6, \ge6$ ) and duration of DPNP (<2 years,  $\ge2$ years).

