6.1. Determination of Sample Size

Approximately 286 patients will be randomized in a 1:1 ratio to duloxetine or pregabalin respectively.

Sample size was calculated in order to have enough statistical power to confirm the non-inferiority of duloxetine to pregabalin based on the primary endpoint, the change from baseline to Week 12 in the weekly mean of the 24-hour average pain score, which will be evaluated using an 11-point NRS in the daily patient diary. Assuming that the treatment difference of the primary endpoint is 0.1 (i.e. duloxetine is superior to pregabalin by 0.1) and that the common standard deviation (SD) of the primary endpoint is 1.82 with a non-inferiority margin of 0.51, 141 patients per group (282, in total) would have a statistical power of 80% to confirm the noninferiority with a 1-sided significance level of 0.025.

The treatment difference could be assumed to be at least 0.1 in this study based on the results such as the double-blind randomized study to comparing duloxetine and pregabalin (the treatment difference [95% confidence interval (CI)]: 0.61 [0.33, 0.90]) (Bouhassira et al. 2014, Marchettini et al. 2016, Tesfaye et al. 2013) and the results of the meta-analysis comparing them indirectly (the treatment difference [95% credible interval]: 0.25 [-0.16, 0.67]) (Quilici et al. 2009) even though there are differences such as treatment periods among the studies.

The noninferiority margin was estimated based on a meta-analysis that applied the DerSimonian-Laird method. Utilizing a phase 3 trial of pregabalin in Japan, which was treated as an evaluation-test in either Japan or the US, this meta-analysis looked at the difference of variation in the average pain score between placebo and pregabalin after 12 weeks of treatment. It was estimated that the difference of the mean value and its 95% CI was 1.03 (0.69, 1.37). The non-inferiority margin for the current study was set using half of the difference of the mean value, 0.51 (that is, 1.03/2). The SD was assumed to be 1.82, based on the pooled analysis results of 1 pregabalin trial and 2 duloxetine trials conducted in Japan.

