6.2. General Considerations

Statistical analysis of this study will be the responsibility of Eli Lilly. Analyses will be conducted using SAS 9.2 (or later).

Efficacy analyses will be conducted on the full analysis set (FAS), unless otherwise stated. The FAS includes all data from all randomized patients receiving at least 1 dose of the study drug according to the treatment the patients were assigned. When mean change from baseline to endpoint is assessed, data will be included in the analysis only if there is a baseline and a corresponding postbaseline measure.

Safety analyses will be conducted on the safety analysis set. This set includes all randomized patients who received at least 1 dose of study drug. Safety analyses will be based on the treatment the patients actually received.

Analyses based on the per-protocol set (PPS) will be performed to examine the robustness of the primary efficacy analysis. The PPS will be defined as a subset of patients in FAS who did not have major protocol deviations.

All tests of hypotheses will be considered statistically significant if the 2-sided p-value is <0.05 , unless otherwise stated. No adjustments for multiple comparisons will be made.

Any change to the data analysis methods described in the protocol will require an amendment ONLY if it changes a principal feature of the protocol. Any other change to the data analysis methods described in the protocol, and the justification for making the change, will be described in the SAP and clinical study report. Additional exploratory analyses of the data will be conducted as deemed appropriate.

Baseline value for a variable will be defined as the last non-missing value for this variable prior to or at randomization visit (Visit 2), unless otherwise specified.

The endpoint value for an efficacy variable is defined as the last non-missing post baseline value prior to or at Visit 6 (Week 12), unless otherwise stated.

The endpoint value for a safety variable is defined as the last non-missing post baseline value prior to or at Visit 7 (Week 13), unless otherwise stated.

In general, descriptive summary statistics will include:

- for categorical variables: number and percentage (with the percentage excluding the number missing in the denominator)
- for continuous variables: number, mean, median, standard deviation, minimum, and maximum.

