6.10. Primary Outcome and Methodology

The primary efficacy variable is the change from baseline in the weekly mean of the 24-hour average pain score measured using an 11-point NRS in the daily patient diary. The weekly mean of the 24-hour average pain score for each week will be the mean score for the following duration:

Week	Duration used for the calculation of weekly mean
Baseline	Day -6 to Day 0
1	Day 2 to 7
2	Day 8 to 14
3	Day 15 to 21
4	Day 22 to 28
5	Day 29 to 35
6	Day 36 to 42
7	Day 43 to 49
8	Day 50 to 56
9	Day 57 to 63
10	Day 64 to 70
11	Day 71 to 77
12	Day 78 to 84

A mixed-model repeated measures (MMRM) analysis will be the primary analytical technique to assess mean change in efficacy measures. The MMRM model will include the random effect of patient and fixed categorical effects of treatment, duration of DPNP (<2 years, ≥2years), week, and treatment-by-week interaction, as well as the continuous fixed covariates of baseline value. An unstructured covariance structure will be used to model the within-patient errors. A Kenward-Rogers correction (Kenward and Roger 1997) will be used to estimate denominator degrees of freedom.

The difference in LS mean between treatments (duloxetine minus pregabalin) at Week 12, along with its 2-sided 95% CI, will be calculated, based on the model. If the upper bound of the 95% CI does not exceed 0.51, it will be concluded that duloxetine is not inferior to pregabalin.

If the model with unstructured covariance structure fails to converge, the sandwich estimator be used to estimate the standard errors of the fixed effects parameters and the model will be fit using covariance structures of the following order until convergence is met:

- heterogeneous toeplitz type = toeph
- heterogeneous autoregressive (1st order) type = arh(1)
- heterogeneous compound symmetric type = cs(h)
- toeplitz type = toep
- autoregressive (1st order) type = ar(1)
- compound symmetric type = cs

If the sandwich estimator is used, the Kenward-Roger approximation for denominator degrees of freedom cannot be used; instead, the denominator degrees of freedom will be partitioned into between-subject and within-subject portions (denoted by DDFM= BETWITHIN in the MODEL statement).

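### Minor: the two responder tests ignore the randomisation strata and rely on the conservative Fisher test, and the PGI-I and CGI-I models have no baseline pain term, so four secondary analyses lose a little precision

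*SAP*

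**What the plan says.** - **Randomisation (Protocol 9.3).** "Randomization will be stratified by baseline weekly mean of the 24-hour average pain score", cut at 6, and also by duration of DPNP, cut at 2 years.
- **Primary analysis (SAP 6.10; Protocol 12.2.6).** The MMRM has treatment, DPNP duration, week and treatment-by-week, "as well as the continuous fixed covariates of baseline value". The supporting ANCOVA also carries duration and baseline.
- **Responders (SAP 6.11; Protocol 12.2.7).** The two documents compare the "proportions of patients achieving each of the following at Visit 6 (Week 12) using Fisher's exact test", for reductions of at least 30% and at least 50%. On missing values the SAP adds: "In this analysis, missing data will be imputed using LOCF method". Neither section names a stratification factor, or an effect estimate with a confidence interval.
- **PGI-I and CGI-I (SAP 6.11; Protocol 12.2.7).** These follow the primary MMRM with visit in place of week, "but without the baseline score in the model for CGI-I and PGI-I". That leaves treatment, DPNP duration, visit and treatment-by-visit.
- **Elsewhere.** No other section gives an adjusted version of these four analyses. The subgroup analysis by baseline pain in SAP 6.14 is optional and covers primary outcomes only.

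**The concern.** Factors used to stratify randomisation are normally carried into the analysis. If such a factor predicts outcome, an unstratified test overstates the variance of the treatment comparison and becomes conservative. Here the primary model respects both strata, the responder tests respect neither, and the PGI-I and CGI-I models respect one. Fisher's test adds conservatism of its own, because its attained size lies below 5%.

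PGI-I and CGI-I rate change since treatment began, so they have no baseline score and removing that term is correct. The gap is that baseline pain, already collected for eligibility and stratification, is not put in its place.

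At stake is some sensitivity in four named secondary comparisons, and an interpretable responder result. In an active-controlled trial, a non-significant p-value says little about how similar two drugs are, whereas a difference with an interval does. The non-inferiority test, its margin and its power are not involved.

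**Working it through.** **Inputs from the documents.** 143 per arm; SD 1.82; margin 0.51; assumed true difference 0.1 in favour of duloxetine; cited differences 0.25 and 0.61 (all SAP 6.1); secondary tests two-sided at 5% (SAP 6.2). **Not in the documents, so assumed and varied:** responder rates, the odds ratio for response between pain strata, and the correlation r of baseline pain with PGI-I or CGI-I.

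**1. The plan's own figure.** For the primary test, n per arm = 2 × 1.82² × (1.960 + 0.842)² / (0.51 + 0.1)² = 139.7, so 140. The noncentral t gives 79.8% power at 140 and 80.1% at 141, which reproduces the stated 141. The documents give no power for the four analyses at issue.

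**2. Fisher against uncorrected chi-square.** The rejection regions for 143 versus 143 were enumerated exactly and weighted by binomial probabilities.
- Size at common rates of 30% to 60%: Fisher 3.6% to 3.8%, chi-square 4.8% to 5.1%.
- Power at an assumed 50% versus 35%: Fisher 68.6%, chi-square 72.7%. This 4-point gap is Fisher's conservatism alone.

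**3. The same comparison at the documents' differences.** A normal shift turns a mean difference d into a responder rate of Φ(Φ⁻¹(base) + d/1.82), with base rates of 30% to 60%.

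| d | Responder difference | Fisher power | Chi-square power |
|---|---|---|---|
| 0.1 | about 2 points | 4.9–5.2% | 6.3–6.7% |
| 0.25 | about 5 points | 11.9–12.7% | 14.6–15.3% |
| 0.61 | 12–13 points | 54.3–57.0% | 59.1–61.7% |

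**4. What stratifying adds.** 100,000 trials were simulated per scenario, with four strata of 36/36/36/35 or 20/34/33/56 per arm and marginal rates held at 50% versus 35%. The addition is the power of Cochran-Mantel-Haenszel (CMH) minus that of chi-square.

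| Odds ratio between pain strata | Added power (points) |
|---|---|
| 1.0 | 0.0 |
| 1.35 | 0.1 |
| 1.65 | 0.3–0.4 |
| 2.0 | about 0.9 |
| 2.7 | about 2.2 |

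CMH size at 40% versus 40% was 4.7% to 5.2%. A separate run had two near-equal strata whose rates differed by 30 points. There Fisher's size fell to about 3.0% while CMH stayed near 5%.

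**5. Baseline pain in the PGI-I and CGI-I models.** A covariate with correlation r multiplies the residual variance by 1 − r². From 80% unadjusted power, the new power is Φ((1.960 + 0.842)/√(1 − r²) − 1.960), and the interval narrows by 1 − √(1 − r²).

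| r | Power | CI narrower by |
|---|---|---|
| 0 | 80.0% | 0% |
| 0.1 | 80.4% | 0.5% |
| 0.2 | 81.6% | 2.0% |
| 0.3 | 83.6% | 4.6% |
| 0.4 | 86.4% | 8.3% |

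The 80% start is only a reference point. Suppose instead that these scales have the primary endpoint's standardised effect. The signal is then z = d / (1.82 × √(2/143)) = d / 0.215, divided by √(1 − r²), and two-sided power is Φ(z − 1.960) + Φ(−z − 1.960).

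| d | r = 0 | r = 0.3 | r = 0.4 |
|---|---|---|---|
| 0.1 | 7.5% | 7.8% | 8.0% |
| 0.25 | 21.3% | 23.0% | 24.5% |
| 0.61 | 80.9% | 84.4% | 87.1% |

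**The case against.** The strongest reply is that this is a preference about a valid, consistent plan.

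- **Source of the responder gain.** Most of it comes from leaving Fisher's test and not from adjusting for pain. Percent reduction is already scaled to baseline, so the pain strata may hardly differ in response, and stratifying would then add almost nothing. This stands.
- **Size of the scenario.** A contrast of 50% versus 35% corresponds to a shift of about 0.70 points, above the largest difference cited in SAP 6.1 (0.61) and seven times the design value. At 0.1, the 1.4 to 1.5 point gap between the tests is little more than their 1.2 to 1.3 point gap under no effect. This also stands, and it is why the gain at the design difference is called negligible.
- **Multiplicity.** SAP 6.2 makes no adjustment across many secondary tests, so a slightly conservative test is defensible. That is reasonable, but incidental conservatism is not error control, and it does not supply the missing interval.
- **PGI-I and CGI-I.** Both scales rate change, so r may be near zero and the gain with it. This is true. The interval narrows only to the extent that r differs from zero.
- **Consistency.** Fisher's test is the plan's usual choice for categorical data, and SAP 6.2 allows further exploratory analyses. A stratified analysis could therefore be added anyway, but it would not be the prespecified one.

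These replies limit the size of the point. They do not show that the present specification is the better one.

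**Conclusion.** The point holds as a minor, optional improvement. Two secondary analyses use neither randomisation stratum and two use only one, although the data are in hand and the primary model uses both.

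For responders, the gain is about 1.5 points of power at a difference of 0.1 and about 5 points at 0.61, nearly all from replacing Fisher's test. Stratification adds at most about 2 points for odds ratios up to 2.7. For PGI-I and CGI-I, the interval narrows by 0.5% to 8.3% for r from 0.1 to 0.4.

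These sizes rest on assumed responder rates, stratum odds ratios and correlations, and on a normal-shift model. The clearest benefit needs none of them: a responder difference with a 95% CI would be reported, where at present no such estimate is named. Nothing here affects the primary conclusion, the 0.51 margin or the stated 80% power.

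**What to change.** In SAP 6.11, and in Protocol 12.2.7 if it is next amended:

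- **Responders.** Compare the proportions with at least 30% and at least 50% reduction by a Cochran-Mantel-Haenszel test stratified by baseline weekly mean 24-hour average pain (<6, ≥6) and DPNP duration (<2, ≥2 years). Report the stratum-adjusted difference in proportions with its 95% CI. The rule for missing data need not change for this.
- **PGI-I and CGI-I.** Include baseline weekly mean 24-hour average pain as a continuous covariate in place of the absent baseline score, and keep DPNP duration.

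The cost is wording and a small programming change, with no new data. Under SAP 6.2 a change of method "will require an amendment ONLY if it changes a principal feature of the protocol", and these secondary analyses are hardly that, so an SAP revision and a justification in the study report should do. The change must be fixed before database lock and unblinding. SAP Version 2 was itself approved on 2 June 2017, shortly before lock. Done later, the stratified results should be labelled post hoc and shown beside the planned ones. All that is given up is Fisher's exact size guarantee, which is worth little at 143 per arm because CMH holds close to 5%.

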#### F1J-JE-HMHA (1413N0841) (d) Clinical Protocol

by the patient. Informed consent must be obtained before any study procedures are performed (Attachment 1). During screening procedures, no study drug will be administered.

**Period 2 - Treatment (12 weeks):** The treatment period will begin at Visit 2 (Day 0) and end at Visit 6 (Week 12). At the beginning of Visit 2 (Day 0), patients will be randomly assigned to duloxetine or pregabalin in a 1:1 ratio. Patients will take duloxetine QD orally after breakfast and pregabalin BID orally as instructed by each respective package label (See Section 9.5). Duloxetine will be administered at 20 mg/day for 1 week and then 40 mg/day for 3 weeks. Pregabalin will be administered at 150 mg/day for 1 week and then 300 mg/day for 3 weeks.

At Visit 4 (Week 4) and at Visit 5 (Week 8), duloxetine and pregabalin doses may be increased in patients who do not achieve  $\geq$ 30 % pain improvement in the BPI-SF average pain score compared with baseline (Visit 2). At either week, duloxetine may be increased to 60 mg/day and pregabalin may be increased to 450 mg/day. If pregabalin is increased to 450 mg/day at Visit 4 (Week 4), it may be further increased to 600 mg/day at Visit 5 (Week 8). See Section 9 for additional dosing details.

Based on clinical judgment and on individual patient tolerability, investigators may decide to keep patients, who don't achieve  $\geq$ 30 % pain improvement, on the original dose (dose escalation is not mandatory). However, efficacy is not expected at lower doses for patients who will not receive dosage increases. From an ethical standpoint, these patients will be considered to discontinue the study in order to select another therapy option following tapering.

Patients will not be allowed to decrease their dose once increased. If patients are unable to tolerate a dosage increase during Period 2, they should be discontinued from the study.

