6.3. Handling of Dropouts or Missing Data

When the imputation for the missing data will be needed, the baseline observation carried forward (BOCF) and last observation carried forward (LOCF) methods will be used for the primary efficacy endpoint. And the LOCF method will be used for the others. The imputation will not be conducted unless otherwise stated.

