6.3.1. Baseline Observation Carried Forward

A BOCF analysis will be performed on the primary variable. For patients discontinuing the study drug due to an adverse event (AE), death or lack of efficacy, the baseline observation will be carried forward to the corresponding primary endpoint evaluation. Otherwise, the last non-missing post baseline observation will be carried forward to the corresponding primary endpoint

for evaluation. Randomized patients without at least 1 post baseline observation will not be included for evaluation with the exception of patients discontinuing study treatment due to an AE, death or lack of efficacy.

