6.3.2. Last Observation Carried Forward

A LOCF analysis will be performed on the primary and the other variables unless otherwise stated. Regardless the patients completed the study or discontinued the study treatment due to any reason, the last non-missing post baseline observation will be carried forward to the corresponding endpoint for evaluation. Randomized patients without at least one post-baseline observation will not be included for evaluation.

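### Week-12 30% and 50% response is imputed by LOCF alone, so some patients who stopped for an adverse event count as responders, and no non-responder version is planned

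*SAP*

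**What the plan says.** SAP 6.11 compares the arms by Fisher's exact test on the proportions reaching at least a 30% and at least a 50% "reduction on the weekly mean of the 24-hour average pain score measured using an 11-point NRS in the daily patient diary". Response is assessed at Visit 6 (Week 12). On missing data it says: "In this analysis, missing data will be imputed using LOCF method". Protocol 12.2.7 gives the same rule.

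SAP 6.3.2 defines LOCF without regard to the reason for stopping. Whether patients completed or "discontinued the study treatment due to any reason, the last non-missing post baseline observation will be carried forward". Randomized patients with no post-baseline value are left out.

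SAP 6.3 sets the scope of the two methods: "the baseline observation carried forward (BOCF) and last observation carried forward (LOCF) methods will be used for the primary efficacy endpoint", followed by "And the LOCF method will be used for the others". SAP 6.3.1 then gives the BOCF rule for the primary variable as follows: "For patients discontinuing the study drug due to an adverse event (AE), death or lack of efficacy, the baseline observation will be carried forward". Other dropouts get their last value. Stops for AE, death or lack of efficacy stay in the BOCF analysis even without a post-baseline value.

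Under SAP 6.10 the primary analysis of the continuous score is an MMRM, with BOCF and LOCF ANCOVAs as robustness checks. No second version of the response analysis is planned.

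**The concern.** Response is meant to describe a patient's status at Week 12. Under LOCF, a patient whose weekly mean had fallen by 30% and who then stopped for an AE is reported as a Week-12 responder, although that patient was no longer on study treatment at Week 12.

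Such stops are foreseeable. Protocol 7.1 does not allow a dose to be lowered once raised, and adds: "If patients are unable to tolerate a dosage increase during Period 2, they should be discontinued from the study". Protocol 6.2 makes the rate of discontinuation for AEs a between-arm comparison in its own right. The plan therefore leaves open whether AE dropout differs between arms, while its only responder comparison can be sensitive to exactly that.

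At stake are the size of the reported responder rates in both arms and, if the arms differ in these stops, the responder difference.

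**Working it through.** **The plan's own figure.** No rate, power or sample size is stated for the response endpoint. The sample size for the primary test (SAP 6.1) reproduces. With margin 0.51, assumed advantage 0.1, SD 1.82, one-sided 0.025 and 80% power, the normal approximation is n = 2 × (1.960 + 0.842)² × 1.82² / (0.51 + 0.1)² = 139.7, so 140 per arm. By noncentral t, power is 79.8% at 140 and 80.1% at 141, which agrees with the stated 141. This has no bearing on the response rule.

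**The same patient under the two rules.** Take a patient who stops for an AE with a last weekly mean at least 30% below baseline.
- LOCF (SAP 6.11, 6.3.2): the reduction at last observation is carried to Week 12, so the patient is a responder.
- The SAP 6.3.1 rule, if applied to response: change is zero, so the patient is a non-responder.

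A patient who stops for an AE with no post-baseline value is dropped under LOCF and kept at zero change under SAP 6.3.1.

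**Formula.** For one arm, let
- d = share stopping for AE, death or lack of efficacy,
- q = share of those whose last weekly mean met the threshold,
- r = response rate in everyone else (other dropouts by LOCF under both rules).

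Then LOCF rate = (1 − d)r + dq, and rate with these stops as non-responders = (1 − d)r. The gap is d × q. The documents give none of d, q or r, so the values below are assumptions.

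**Rise per arm, with 143 patients per arm (SAP 5):**

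| d | q = 20% | q = 40% | q = 60% |
|---|---|---|---|
| 10% | 2 points (2.9 patients) | 4 points (5.7) | 6 points (8.6) |
| 20% | 4 points (5.7) | 8 points (11.4) | 12 points (17.2) |

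This takes every such stop to have a post-baseline value. If a share e of the arm stops for these reasons without one, LOCF also divides by 1 − e instead of 1, which raises the reported rate relative to counting those patients as non-responders.

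**Between-arm difference.** The shift is d × q in arm A minus d × q in arm B. With equal d and equal q it is zero. With d = 20% in arm A, 10% in arm B, and r = 50% in both:

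| q (both arms) | LOCF, A vs B | Difference | Stops as non-responders, A vs B | Difference |
|---|---|---|---|---|
| 20% | 44% vs 47% | −3 points | 40% vs 45% | −5 points |
| 40% | 48% vs 49% | −1 point | 40% vs 45% | −5 points |
| 60% | 52% vs 51% | +1 point | 40% vs 45% | −5 points |

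Unequal q is enough on its own: with d = 10% in both arms and q = 60% versus 20%, the shift is 6 − 2 = 4 points.

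**Scale.** With 143 per arm and rates near 50%, the 95% CI half-width for a difference is 1.96 × √(2 × 0.25 / 143) = 0.116, about 12 points.

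**The case against.** The plan is consistent with itself. A reader might infer that LOCF for response contradicts the BOCF rule in SAP 6.3.1. It does not: SAP 6.3 limits BOCF to the primary endpoint and assigns LOCF to the rest, and Protocol 12.2.7 agrees with SAP 6.11. LOCF is also one of the two robustness analyses of the primary variable. That stands.

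Nor does LOCF count everyone who stops for an AE or lack of efficacy as a responder. It counts only those past the threshold at their last weekly mean, and few who stop for lack of efficacy will be. The design may lower q further. Increases at Weeks 4 and 8 are offered only to patients below 30% improvement on the BPI-SF average pain item, so those who cannot tolerate these increases were below that level when they were offered. That stands in part: BPI-SF is not the diary score, pain may improve before the stop, and the Week 1 increase applies to everyone, so AE stops in the first four weeks have no such filter.

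A reader might also infer that the comparison is biased in favour of the arm with more dropouts. That holds only relative to the non-responder definition, and only if d × q differs between arms. In most of the illustrated cases the arm with more stops still does worse under LOCF, by a smaller amount. Shifts of 2 to 6 points are also within the sampling error of about 12 points.

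Finally, discontinuation reasons are compared between arms (SAP 6.4), AEs leading to discontinuation are summarised (SAP 6.13.2), and the continuous score has its BOCF check. These let a reader see whether AE dropout matters, but they do not show a responder rate free of it.

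**Conclusion.** The point holds as a gap in a secondary analysis. The 30% and 50% response at Week 12 is analysed in one way only. That way credits threshold-meeting patients who stopped, mainly for AEs, and drops those who stopped before any post-baseline value. The continuous form of the same diary variable is protected by a BOCF check; response is not.

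The effect is a rise of d × q in each arm's rate: about 2 to 12 points, or roughly 3 to 17 patients of 143, for assumed d of 10–20% and q of 20–60%. A low q, which is plausible for lack-of-efficacy stops, puts it near the bottom of that range. The between-arm difference may not move at all; under the assumed 20% versus 10% it moves by 2 to 6 points and can change sign at the top of the range of q.

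It would be wrong to read this as a threat to the main result. Non-inferiority rests on the MMRM of the continuous score, and response is one of several secondary endpoints without multiplicity adjustment.

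**What to change.** In SAP 6.11, count patients who discontinue Period 2 for AE, death or lack of efficacy as non-responders at Week 12, including those with no post-baseline diary value. Keep LOCF as the sensitivity analysis. At minimum, report the non-responder version beside LOCF for both thresholds. Settle this before unblinding.

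The cost is one sentence and one derivation, since the BOCF analysis in SAP 6.3.1 already needs the discontinuation reasons. Because LOCF is also written into Protocol 12.2.7, the change and its reason must be recorded in the SAP and the study report, as SAP 6.2 requires for changes that do not alter a principal feature of the protocol. The downside is that reported responder rates fall in both arms.
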